4.9. Safety Analyses

All safety analyses will be conducted on the Safety Population.

Adverse Events

Adverse events will be coded using the MedDRA Version 24.0 - Mar 2021 and displayed in tables and listings using System Organ Class (SOC) and Preferred Term (PT).

Analyses of adverse events will be performed for those events that are considered treatment emergent adverse events (TEAE), where treatment emergent is defined as any adverse event with onset on or after the first dose of study medication through the end of the study or any event that was present at baseline but worsened in intensity or was considered drug-related by the investigator through the end of the study.

The safety will be assessed by incidence of TEAEs, therefore, in any tabulation, a subject contributes only once to the count for a given adverse event (SOC or preferred term). An overall summary of TEAEs will be presented including the number of events and the number of the subjects with events along with percentages by treatment group and overall. The overall summary will include subjects with AE leading to death, subjects with TEAEs leading to insert removal and subjects with TEAEs leading to subject withdrawal. In summary tables, SOC will be presented alphabetically and events within SOC will be presented by decreasing frequency count based on the total column.

The frequency and percentage of subjects with any TEAEs and separately for ocular and nonocular TEAEs, with any ocular TEAEs by relationship to treatment (unrelated, related), with any ocular serious TEAEs by relationship to treatment (unrelated, related), with any TEAE by severity (mild, moderate, or severe), and with any serious adverse event (SAE) and separately for ocular and non-ocular events will be summarized by treatment group and overall.

All adverse events will be listed in subject data listings.

By-subject listings also will be provided for the following: subject deaths; serious adverse events; and adverse events leading to withdrawal.

Non-AE Safety Analyses

The following safety assessments will be summarized using descriptive statistics for Safety population by treatment group and overall. Assessments will be presented for study eye and non-study eye separately.

Sponsor:	Ocular Therapeutix, Inc.		
Protocol:	CLN-Protocol-0054		
Document Version No.:	V1.0 Document Date:		01-OCT-2021

1- Best Corrected Visual Acuity (BCVA)

LogMAR Visual Acuity (VA) score for each visit, its CFB, and loss of 3 Lines or more in BCVA LogMAR Score from Baseline at each post-baseline visit will be calculated and summarized using descriptive statistics.

2- Slit-Lamp biomicroscopy

The evaluation of normal, mild, moderate, severe, and very severe for each eye in Eyelid Vascularity (vascular engorgement) and Vascular Engorgement of Eyelid Margin of upper and lower lid, as well as normal, abnormal non-clinically significant, and abnormal clinically significant for each eye in Punctal Appearance, Lid Apposition, Lashes, Conjunctiva, Sclera, Cornea, Anterior Chamber, Iris, Pupil, and Lens will be tabulated for each visit by using the frequency and percentage.

3- Intraocular Pressure (IOP) measurement (mmHg)

Absolute value at baseline and visit 8 (week 16), its CFB, absolute IOP measurement \geq 30 mmHg at each visit, and CFB in IOP > 5 mmHg as well as >10 mmHg at Visit 8 will be summarized using descriptive statistics.

4- Fundus Examination

The evaluation of normal, abnormal non-clinically significant, and abnormal clinically significant for each eye in vitreous, retina, macula, choroid, and optic nerve exam will be tabulated for visit 1 and visit 8 by using the frequency and percentage. The absolute cup-to-disc ratio at baseline and Visit 8 (Week 16) and its CFB at Visit 8 (Week 16) will be presented using descriptive statistics.

5- Artificial tears use during the study

The use of artificial tears, based on the Daily Subject Diary, since last visit will be tabulated for each post-baseline visit by using frequency and percentage. Number of times AT used since last visit will be reported among all subjects who have any daily subject dairy data since the last visit using descriptive statistics.

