6.2 Study Endpoints

6.2.1 Safety Evaluations (Cohorts 1 and 2)

Primary:

• Non-ocular and Ocular Adverse Events (AEs)

Secondary:

- Best-Corrected Visual Acuity (BCVA)
- Slit Lamp Biomicroscopy (including punctum assessment)
- Intraocular Pressure (IOP)
- Fundus Examination
- Artificial tears use during the study

6.2.2 Efficacy Endpoints (Cohort 2 only):

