10.4 Monitoring and Recording of AEs and SAEs

10.4.1 Adverse Events

Any AE experienced by the subject from Visit 2 (Insertion/Day 1) through Visit 9 (30-day follow-up visit) is to be recorded in the eCRF, regardless of the severity of the event or its relationship to study treatment.

Any AEs already documented at a previous assessment and designated as ongoing, should be reviewed at subsequent visits, as necessary. If these have resolved, this should be documented.

Changes in intensity or frequency of AEs should be recorded as separate events (i.e., a new record started).

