1. INTRODUCTION AND OBJECTIVES OF ANALYSIS

1.1. Introduction

Dry Eye Disease (DED)

Dry eye disease (DED), also known as Keratoconjunctivitis Sicca (KCS), is one of the most common ophthalmic disorders presenting to the clinician (American Academy of Ophthalmology, 2018). Prevalence of dry eye is higher among women than men (Farrand et al, 2017). Prevalence also increases with age with 2.7% of Americans age 18 to 34 years and 18.6% of Americans ≥75 years diagnosed with DED (Farrand et al, 2017).

DED is a multifactorial disorder of the tear film and ocular surface that results in eye discomfort, visual disturbances, tear film instability, and often ocular surface damage (Perry, 2008; Schultz, 2014). In humans, dry eye was found to be associated with the presence of conjunctival T-cells and elevated levels of inflammatory cytokines in the tears compared with controls (Massingale et al, 2009; Lee et al, 2013).

Investigational Product Rationale

In order to address the limitations of topical ophthalmic eye drops, Ocular Therapeutix has developed OTX-CSI (cyclosporine ophthalmic insert) for intracanalicular use. OTX-CSI combines the benefits of cyclosporine with punctal occlusion, an effective therapy for DED (McCabe, 2009). OTX-CSI contains approximately 0.36 mg of cyclosporine and is designed to deliver therapeutic levels of cyclosporine onto the ocular surface for a duration of approximately 12 weeks. Continuous release of cyclosporine from the hydrogel inserts may result in higher daily concentrations of cyclosporine delivered to the ocular surface than is found with topical Restasis.

Considering the low cyclosporine concentrations required at the ocular surface, OTX-CSI, offers promise as a potential sustained release treatment for patients with signs and symptoms of DED for approximately 12 weeks with a single insert.

The two active formulations of OTX-CSI being studied in this clinical trial contain the same cyclosporine dose and release drug at the same daily rates but differ in their hydrogel composition. These two formulations are designed to have different breakdown periods of the hydrogel with one formulation designed to last approximately 2 to 3 months (Formulation 1 (F1)) and the other approximately 3 to 4 months (Formulation 2A (F2A)).

Sponsor:	Ocular Therapeutix, Inc.			
Protocol:	CLN-Protocol-0054			
Document Version No.:	V1.0	Document Date:	01-OCT-2021	

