2. STUDY DESIGN

2.1. Synopsis of Study Design

This is a randomized, multi-center, double-masked, vehicle-controlled, phase 1/2 clinical study designed to evaluate the safety, tolerability, and efficacy of OTX-CSI (cyclosporine ophthalmic insert) for intracanalicular use for the treatment of subjects with DED. Approximately 145 subjects (290 eyes) will be enrolled in this study at approximately 15 sites in the US.

Subjects will be enrolled in two cohorts. Cohort 1 will be an open-label group consisting of approximately 5 subjects. Cohort 2 will be a randomized, double-masked group consisting of approximately 140 subjects treated with 2 different hydrogel formulations of OTX-CSI and 2 different formulations of hydrogel vehicle inserts (HV). Both eyes will be treated with the same treatment/formulation.

Cohort Number	Number of Subjects	Treatment	Formulation
1 Open-label	5	OTX-CSI	2A
2 Randomized, double-masked	40	OTX-CSI	1
	40	OTX-CSI	2A
	40	HV	2B
	20	HV	3

Cohort 1

Subjects in Cohort 1 will undergo Screening 14 days prior to Insertion/Day 1 (Visit 2) to determine eligibility and eligibility will be re-confirmed at Visit 2 (Insertion/Day 1). The treatment follow-up visits will occur at Week 2 (Visit 3), Week 4 (Visit 4), Week 6 (Visit 5), Week 9 (Visit 6), Week 12 (Visit 7), and Week 16 (Visit 8). All subjects in Cohort 1 will be followed until Week 16 (Visit 8) whether or not an insert is visualized.

Cohort 2

Subjects in Cohort 2 will undergo Screening 14 days prior to Insertion/Day 1 (Visit 2) to determine eligibility. At Visit 2 (Insertion/Day 1) eligibility will be confirmed and subjects who are eligible will be randomly assigned to one of four treatment groups (OTX-CSI Formulation 1, OTX-CSI Formulation 2A, HV Formulation 2B or HV Formulation 3) in a 2:2:2:1 ratio. Should only a unilateral insertion be possible, Visit 2B will occur within 3 days to attempt the insertion again. The treatment follow-up visits will occur at Week 2 (Visit 3), Week 4 (Visit 4), Week 6 (Visit 5),

Sponsor:	Ocular Therapeutix, Inc.			
Protocol:	CLN-Protocol-0054			
Document Version No.:	V1.0	Document Date:	01-OCT-2021	

Week 9 (Visit 6), Week 12 (Visit 7), and Week 16 (Visit 8). All subjects in Cohort 2 will be followed until Week 16 (Visit 8) whether or not an insert is visualized.

[figure not shown]

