For both cohorts, if an OTX-CSI or HV insert is visualized in either eye or both eyes at Week 16 (Visit 8) the subject will return to the clinic in 30 days (\pm 10 days; Visit 9) and will continue returning to the clinic every 30 days as needed until an insert can no longer be visualized and the physician has determined that there is no evidence of biological activity. Additionally, subjects may be exited any time at the investigator's discretion. If an OTX-CSI or HV insert cannot be visualized at Week 16 (Visit 8) and the physician has determined that there is no evidence of biological activity, the subject will exit the study.

This study will be conducted per the schedule shown in Figure 1.

[figure not shown]
Statistical Analysis Plan

Sponsor:	Ocular Therapeutix, Inc.			
Protocol:	CLN-Protocol-0054			
Document Version No.:	V1.0	Document Date:	01-OCT-2021	

Figure 1 Cohort 1 and Cohort 2 Study Schematic

^{*}Subject remains in study until insert is no longer visible and no evidence of biological activity.

CRS-BS-TP-000005 V 1.0

Page 15 of 50

Client / Cytel Confidential: This is a controlled document and shall not be changed, saved, copied or reproduced by any unauthorized person.

Sponsor:	Ocular Therapeutix, Inc.			
Protocol:	CLN-Protocol-0054			
Document Version No.:	V1.0 Document Date: 01-OCT-2021			

2.2. **Objectives of Statistical Analysis**

The objectives of the trial with respect to Cohort 1 are to assess the safety and tolerability of OTX-CSI in subjects with DED. The objectives of the trial with respect to Cohort 2 are to assess the safety, tolerability, and efficacy of OTX-CSI in subjects with DED.

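### Treatment-emergent AEs are counted to the end of the study, but follow-up after Week 16 depends on insert persistence or biological activity, so the crude AE percentages cover different observation times by formulation

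*SAP*

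**What the plan says.** AEs, ocular and non-ocular, are the primary safety evaluation (Protocol 6.2.1). SAP 4.9 counts as treatment-emergent "any adverse event with onset on or after the first dose of study medication through the end of the study", together with baseline events that later worsen or are judged drug-related. It summarizes them as numbers and percentages of subjects by treatment group and overall.

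Follow-up is described in SAP 2.1 (and Protocol 6.1). To Week 16 it is common: "All subjects in Cohort 2 will be followed until Week 16 (Visit 8) whether or not an insert is visualized". After Week 16 it is conditional. A subject with an insert visible in either eye comes back after 30 days (±10) and "will continue returning to the clinic every 30 days as needed until an insert can no longer be visualized", with the further requirement that the physician finds no evidence of biological activity. The exit rule opens with "If an OTX-CSI or HV insert cannot be visualized at Week 16 (Visit 8) and the physician has determined that there is no evidence"; what must be absent is biological activity, and a subject who meets both conditions leaves the study. Investigators may also exit a subject at any time.

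The designed life of the inserts differs by arm (SAP 1.1): F1 about 2 to 3 months, F2A and F2B about 3 to 4 months, F3 about 1 week.

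On recording, Protocol 10.4.1 states: "Any AE experienced by the subject from Visit 2 (Insertion/Day 1) through Visit 9 (30-day follow-up visit) is to be recorded in the eCRF". Protocol 8.3.10 repeats the 30-day visit, with AE recording, for as long as it is needed.

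**The concern.** Who remains under observation after Week 16 is decided by a post-randomization feature, insert persistence, that the formulations were designed to differ on. The crude percentage of subjects with an event can only rise with time observed. If two arms are observed for different lengths of time, their percentages differ even when the underlying event rates are the same.

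I found nothing in either document that equalizes the window. There is no Week 16 cut-off for AEs, no rate per subject-time and no definition of the end of the study. Insert exposure is tabulated separately (SAP 4.6, Table 14.1.8) and is not linked to the AE tables. By contrast, IOP change and the follow-up fundus examination are tied to Visit 8.

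Safety and tolerability are stated objectives for Cohort 2, and the arms are small (40/40/40/20). Readers will judge the formulations from these columns. The distortion could make a longer-lasting insert look slightly less safe than F3, or make F1 look slightly safer than the long-acting vehicle F2B.

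**Working it through.** **The plan's own figure.** Protocol 6.5 gives about 18 weeks of participation. Screening of 14 days plus 16 weeks is 2 + 16 = 18 weeks. This fits subjects who exit at Week 16. A subject with a visible insert has at least one more visit, 20 to 40 days later.

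**Where Week 16 falls.** Week 16 is day 112. With a month of 365.25/12 = 30.44 days, that is 112/30.44 = 3.68 months. The designed life is:

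- F3: 7 days, gone by day 112
- F1: 61 to 91 days, gone by day 112
- F2A and F2B: 91.3 to 121.8 days, so day 112 lies inside the range

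**Share still holding an insert.** The documents give no retention figure, so I assume persistence is uniform over the designed range.

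- Per eye, F2A/F2B: (121.8 − 112)/(121.8 − 91.3) = 0.32. Over the ±3-day visit window this is 0.42 at day 109 and 0.22 at day 115.
- Per subject, because either eye triggers return: 0.32 if the two eyes are fully correlated, and 1 − (1 − 0.32)² = 0.54 if they are independent.
- F1 and F3: 0.

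**Extra observation time.** One 30-day visit adds 30/112 = 27% for a retained subject (18% for 20 days, 36% for 40 days). The arm mean rises by 0.32 × 30/112 = 8.6% to 0.54 × 30/112 = 14.4%.

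**Effect on crude incidence.** Assume equal, constant hazards in all arms and Week 16 incidence p. A retained subject's incidence at day 142 is 1 − (1 − p)^(142/112). With share q retained, the arm reads p + q × (day-142 incidence − p). For p = 30%, the day-142 incidence is 1 − 0.7^(142/112) = 36.4%.

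| Week 16 incidence (F1, F3) | F2A/F2B, q = 0.32 | q = 0.54 | q = 1 |
|---|---|---|---|
| 10% | 10.8% | 11.3% | 12.5% |
| 30% | 32.0% | 33.4% | 36.4% |
| 50% | 52.7% | 54.6% | 58.5% |

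At p = 30%, combined OTX-CSI (equal F1 and F2A) reads (30.0 + 32.0)/2 = 31.0% to (30.0 + 33.4)/2 = 31.7%. F2B reads 32.0% to 33.4% and F3 reads 30.0%. The pooled column therefore matches neither vehicle.

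**In subjects.** 2.0 to 3.4 points of 40 is 0.8 to 1.4 subjects per arm.

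**With a Week 16 cut-off** the scheduled window is the same in every arm, and the artefact under these assumptions is 0 points.

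**The case against.** The strongest reply is that the effect is small and rests on assumptions. Neither document gives retention at Week 16 or the timing of AEs. Protocol 4.4 lists many risks tied to the insertion procedure. If events cluster there, the hazard after Week 16 is lower and the artefact is smaller than shown. Even as computed, it is about one subject in an arm of 40, against a binomial standard error of √(0.3 × 0.7/40) = 7 points. This stands, and it limits the weight of the point.

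A second reply is that counting through the whole period of insert presence is a legitimate safety summary for a longer-lasting product, and that the exposure table and AE listings let a reader see the imbalance. This also stands, and it is a reason to keep the end-of-study counts. It does not make those counts comparable between arms.

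A third reply concerns the remedy. A window ending at Week 16 or earlier exit does not correct for differential dropout, and a table of late events has a denominator selected by persistence. Both are true. Subject-time should therefore accompany the tables, and the late-event table cannot support an arm comparison.

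The documents do not support several stronger readings that a reader might infer:

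- That only F2A v F2B is balanced. F1 and F3 should both be gone by Week 16, so F1 v F3 is roughly balanced too.
- That a planned F1 v F2A comparison is compromised. SAP 5 says the difference between the two OTX-CSI formulations will not be studied.
- That a visible insert is the sole route to longer follow-up. Exit at Week 16 also requires no evidence of biological activity.
- That the gap keeps growing with each further visit. Protocol 10.4.1 records AEs through Visit 9, while the 30-day visit repeats, so whether later events count is unsettled.

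**Conclusion.** The point holds as a matter of presentation. The schedule builds in longer observation for F2A and F2B, the AE percentages run to the end of the study, and nothing in the plan adjusts for the difference. The comparisons affected are F1 v F2B, F2A v F3 and combined OTX-CSI v either vehicle.

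The likely size is about 2 to 3.4 points at a 30% Week 16 incidence, and 6.4 points if every F2A/F2B subject were retained. These figures assume uniform persistence over the designed range, constant hazard and one extra 30-day visit. A reader might infer that the trial's error rates or its safety conclusions are compromised. The documents do not support that: no between-arm AE test is planned, and the artefact is small beside sampling error. The change is worth making because it is cheap and removes a design-driven difference from the primary safety evaluation.

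**What to change.** In SAP 4.9:

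1. Present the between-arm TEAE tables (14.3.1 to 14.3.5) for events with onset through the Week 16 visit, or earlier exit, as the main comparison.
2. Keep the end-of-study counts as a second presentation, and show subject-time under observation, or events per subject-time, by arm.
3. List events after Week 16 by arm with the number of subjects still under observation, labelled as description only.
4. Define the end of the study for AE counting, and reconcile the Visit 9 limit in Protocol 10.4.1 with the repeating 30-day visits in Protocol 8.3.10.

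The dates needed are already collected, no event is dropped and trial conduct does not change. The cost is SAP wording and one extra table split, with slightly fewer events in the main tables.

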4.4 Risk-Benefit Analysis

OTX-CSI has the potential to deliver an efficacious cyclosporine dose to the ocular surface as a sustained release treatment for patients with signs and symptoms of DED; the dose selected is based on pre-clinical and clinical data. The risks associated with OTX-CSI have been minimized by formulating the ophthalmic insert with constituents that have a long history of use in medical devices and pharmaceuticals. Furthermore, results of biocompatibility and preclinical testing at a comparable dose, which will be used in the clinic, confirmed that OTX-CSI has no difference in inflammatory or toxic response of ocular tissues in the canine model compared with controls.

The most common adverse events (AEs) associated with topical cyclosporine (see Appendix 1 Cyclosporine Package Insert in the Investigator's Brochure)

- Ocular burning (17%)
- Conjunctival hyperemia (1-5%)
- Discharge (1-5%)
- Epiphora (1-5%)
- Eye pain (1-5%)
- Foreign body sensation (1-5%)
- Pruritus (1-5%)
- Stinging (1-5%)

• Visual disturbance (most often blurring; 1-5%)

The following adverse reactions have also been identified during post approval use of Restasis[®]: hypersensitivity (including eye swelling, urticaria, rare cases of severe angioedema, face swelling, tongue swelling, pharyngeal edema and dyspnea) and superficial injury of the eye (from the vial tip touching the eye during administration). Since these reactions are voluntarily reported by a population of an uncertain size, it is not always possible to reliably estimate their frequency or establish a causal relationship to drug exposure.

The following AEs and/or risks have been observed with the insertion procedure:

- Perforation of or trauma to the punctum and/or surrounding tissues
- Punctoplasty
- Tearing or epiphora
- Eye inflammation
- Allergic reaction
- Dacrocystitis
- Canaliculitis
- Eye pain and discomfort, including foreign body sensation
- Decreased/impaired visual acuity
- Tearing with mucopurulent discharge
- Stenosis
- Inability to remove test article
- Infection or intraocular infection that if severe could lead to temporary or permanent impairment of eyesight
- Need for surgery on the lacrimal system

Overall, the risk-benefit analysis supports the evaluation of OTX-CSI and HV inserts as planned for administration in this trial.

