2.6.2. Safety Variables

The safety variables are as follows:

- 1- Ocular and non-ocular adverse events
- 2- Best Corrected Visual Acuity (BCVA): LogMAR Visual Acuity (VA) score at each visit and its CFB at each post-baseline visit
- 3- Slit-Lamp biomicroscopy parameters by location (Eyelid Vascularity (vascular engorgement), Vascular, Engorgement of Eyelid Margin of upper and lower lid, Punctal Appearance, Lid Apposition, Lashes, Conjunctiva, Sclera, Cornea, Anterior Chamber, Iris, Pupil, Lens) by visit
- 4- Intraocular Pressure (IOP) measurement (mmHg) and its CFB by visit
- 5- Fundus Examination: Vitreous, Retina, Macula, Choroid, Optic nerve by visit
- 6- Artificial tears use during the study: the use of Artificial tears since last visit at each postbaseline visit.

Sponsor:	Ocular Therapeutix, Inc.			
Protocol:	CLN-Protocol-0054			
Document Version No.:	V1.0 Document Date: 01-OCT-2021			

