Document Version No.:	V1.0	Document Date:	01-OCT-2021

- Table 14.3.4.2 Non-Ocular Treatment-Emergent Adverse Events (TEAEs) Related to IP by System Organ Class and Preferred Term – SAFETY
- Table 14.3.4.3: Ocular Serious Treatment-Emergent Adverse Events (TEAEs) Related to IP by System Organ Class and Preferred Term – SAFETY
- Table 14.3.4.4: Non-Ocular Serious Treatment-Emergent Adverse Events (TEAEs) Related to IP by System Organ Class and Preferred Term – SAFETY
- Table 14.3.5.1: Maximum Severity of Ocular Treatment-Emergent Adverse Events (TEAEs) by System Organ Class and Preferred Term – SAFETY
- Table 14.3.5.2: Maximum Severity of Non-Ocular Treatment-Emergent Adverse Events (TEAEs) by System Organ Class and Preferred Term – SAFETY
- Table 14.3.6.1: Summary of Best Corrected Visual Acuity (BCVA) LogMAR VA Score and Change from Baseline on Study Eye by Visit SAFETY
- Table 14.3.6.2: Summary of Best Corrected Visual Acuity (BCVA) LogMAR VA Score and Change from Baseline on Non-Study Eye by Visit SAFETY
- Table 14.3.7.1: Summary of Intraocular Pressure (IOP) (mmHg), IOP ≥ 30 mmHg and Change from Baseline (CFB), CFB IOP >5 mmHg and >10 mmHg on Study Eye by Visit – SAFETY
- Table 14.3.7.2: Summary of Intraocular Pressure (IOP) (mmHg), IOP ≥ 30 mmHg and Change from Baseline (CFB), CFB IOP >5 mmHg and >10 mmHg on Non-Study Eye by Visit – SAFETY
- Table 14.3.8.1: Summary of Slit-Lamp Biomicroscopy Results on Study Eye by Location and Visit SAFETY
- Table 14.3.8.2: Summary of Slit-Lamp Biomicroscopy Results on Non-Study Eye by Location and Visit SAFETY
- Table 14.3.9.1: Summary of Fundus Examination Results on Study Eye by Visit SAFETY
- Table 14.3.9.2: Summary of Fundus Examination Results on Non-Study Eye by Visit SAFETY

Table 14.3.10: Summary of Artificial Tear Use from Baseline by Visit – SAFETY

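### Slit-lamp findings are summarised only as per-visit percentages, so the tables cannot show how many eyes became worse than their own baseline

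*SAP*

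**What the plan says.** SAP 2.6.2 item 3 defines the slit-lamp variable by location, ending "Conjunctiva, Sclera, Cornea, Anterior Chamber, Iris, Pupil, Lens) by visit". SAP 4.9 item 2 gives the method. Lid vascularity is reported in five grades from normal to very severe. The remaining structures are reported as normal, abnormal but not clinically significant, or abnormal and clinically significant. The analysis is then: "Iris, Pupil, and Lens will be tabulated for each visit by using the frequency and percentage". The planned output in SAP 7.1 matches: "Summary of Slit-Lamp Biomicroscopy Results on Study Eye by Location and Visit SAFETY" (Table 14.3.8.1), with Table 14.3.8.2 for the non-study eye. Neither SAP section 5 nor the protocol adds a shift table or a count of worsened eyes.

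Other ocular safety measures in the same section are compared with baseline. For visual acuity the plan is "LogMAR Visual Acuity (VA) score for each visit, its CFB, and loss of 3 Lines or more in BCVA LogMAR Score from Baseline". For intraocular pressure it includes "CFB in IOP > 5 mmHg as well as >10 mmHg at Visit 8 will be summarized using descriptive statistics". Cup-to-disc ratio also has a change from baseline. The fundus categories in item 4 are, like slit lamp, tabulated by visit only.

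**The concern.** The protocol (6.2.1) lists slit lamp, including punctum assessment, as a secondary safety evaluation. The examination could show several of the procedure risks in protocol 4.4, among them eye inflammation, stenosis and "Perforation of or trauma to the punctum and/or surrounding tissues".

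Participants have dry eye. The qualifying eye must have total corneal staining of at least 6 at screening and at least 5 at Day 1. Some corneal, conjunctival and lid findings may therefore be abnormal before insertion, and some may improve. A per-visit percentage nets the eyes that improve against the eyes that deteriorate. The safety reader wants the second group on its own, by treatment group, and the planned tables do not separate it.

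**Working it through.** The plan states no figure for slit-lamp findings and no formal sample size calculation, so there is nothing to reproduce. The planned Cohort 2 arms (SAP 2.1) are 40, 40, 40 and 20 subjects, and each subject contributes one study eye. All abnormality rates below are assumptions.

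**1. What a per-visit table fixes.** For one structure and one arm with complete data:

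abnormal at follow-up = abnormal at baseline − resolved + new.

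If a of n eyes are abnormal at both visits, resolved equals new. New cases can come only from the n − a eyes normal at baseline, and resolved cases only from the a abnormal eyes. The number of new cases can therefore be anything from 0 to min(a, n − a).

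| n | a at both visits | n − a | New eyes compatible with the table |
|---|---|---|---|
| 40 | 8 (20%) | 32 | 0 to 8 |
| 40 | 16 (40%) | 24 | 0 to 16 |
| 40 | 24 (60%) | 16 | 0 to 16 |
| 20 | 4 (20%) | 16 | 0 to 4 |
| 20 | 8 (40%) | 12 | 0 to 8 |
| 20 | 12 (60%) | 8 | 0 to 8 |

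**2. A less extreme range.** Suppose 25% or 50% of the abnormal eyes improve and an equal number become abnormal, so the per-visit percentage does not move. For n = 40:

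| Abnormal at baseline | 25% improve: new / baseline-normal | 50% improve: new / baseline-normal |
|---|---|---|
| 8 | 2/32 = 6.25% | 4/32 = 12.5% |
| 16 | 4/24 = 16.7% | 8/24 = 33.3% |
| 24 | 6/16 = 37.5% | 12/16 = 75.0% |

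An unchanged percentage would then conceal 2 to 12 new cases of 40 eyes (5% to 30% of all eyes). In an arm of 20, the same assumptions give 1 to 6.

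**3. Distinct eyes over time.** If 1 of 40 eyes is abnormal at each of the six visits from Visit 3 to Visit 8, the table reads 1/40 six times. That could be one persistent finding or six different eyes. This ambiguity needs no baseline abnormality, so it applies to the punctum as well.

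**4. Whether the data allow better.** Slit lamp is scheduled at Visits 1 and 2 and at every later scheduled visit (protocol Appendix 1). The categories are ordered (protocol Appendix 9). SAP 4.2.1 defines baseline as the last available value before treatment. A within-eye shift can be derived from what is already collected.

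**The case against.** The strongest reply is that worsening is already captured elsewhere.

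- **Adverse events.** These are the primary safety evaluation. Protocol 10.1 counts new conditions and exacerbations, and SAP 4.9 treats an event that worsens from baseline as treatment-emergent. Ocular events are tabulated by term, relationship and maximum severity. This stands in part: it depends on the investigator reporting the finding as an event, and no rule ties a change in slit-lamp category to such a report.
- **Listing 16.1.18.** It shows every result, and protocol Appendix 9 requires an explanation for each abnormal finding. The listing is not summarised by arm.
- **Staining.** Corneal and conjunctival staining have change-from-baseline analyses in both eyes. They cover the structures where netting is most plausible, but only as dye scores and group means.

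A reader might infer three stronger things that the documents do not support.

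- *That treatment-emergent worsening is not reported at all.* The adverse event tables report it. What is missing is a same-eye summary of the examination itself.
- *That a chance imbalance at baseline would pass as a treatment effect.* The pre-insertion visits stand in the same tables, by treatment group, so an imbalance would be visible.
- *That improving dry eye would hide punctal or anterior-segment harm.* This is much less plausible. Protocol 7.2 excludes uveitis, active ocular infection, nasolacrimal duct obstruction and confounding lid anatomy. Protocol 8.3.2 calls for a check of the punctum before insertion. Most abnormal findings there should be new. The staining criterion also binds only the qualifying eye.

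It is also fair to say that visual acuity, pressure and cup-to-disc ratio are numeric, and that the categorical fundus results get the same treatment as slit lamp. The contrast is largely numeric against categorical.

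**Conclusion.** The point holds as a reporting gap in a secondary safety variable. The planned slit-lamp tables permit comparison of group percentages across visits, but they cannot separate new from resolved findings or count the distinct eyes that worsened. With 16 of 40 eyes abnormal at both visits, 0 to 16 could be new.

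The calculations show what the tables leave open. They do not show that cancellation will occur, since the documents give no baseline, resolution or onset rates. The practical weight falls on cornea, conjunctiva and lid vascularity; for the other structures the main loss is the count of distinct eyes. No test or efficacy analysis is affected. This is an improvement worth making, not a flaw that threatens the trial's conclusions.

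**What to change.** In SAP 4.9 item 2, and alongside Tables 14.3.8.1 and 14.3.8.2, add a shift table for each structure, eye and treatment group:

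- from baseline as defined in SAP 4.2.1, not Visit 2 alone, so that an eye with only a Visit 1 result is kept;
- to each post-baseline visit and to the worst post-baseline result;
- with the number and percentage of eyes that worsen: normal to abnormal, any change to clinically significant, or at least 1 grade for lid vascularity;
- over eyes with both a baseline and a post-baseline result, with that denominator printed, because it will still vary by visit.

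The fundus categories in item 4 can be handled the same way.

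The cost is programming and several more pages of descriptive output, given the number of structures, two eyes and six or more visits. If length is a concern, the worst-post-baseline shift carries most of the information. No new data, visits or tests are needed, and no clinical procedure changes.
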